13.2 SAS Code Example for ANOVA

Proc Mixed can be used to analyze the crossover design data as follows:

```
proc mixed data=XXXX;
class sequence patient period treatment;
model Response= sequence patient period treatment /solution
ddfm=satterth;
random patient(sequence);
lsmeans drug / pdiff cl e;
run;
```

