9.1.1.2 Randomization Phase (HV Cohort)

Subjects who continue to meet the eligibility criteria will be randomized to treatment sequence A, B or C consisting of 3 Treatment Periods, 1-night duration each: lemborexant 10 mg, lemborexant 25 mg, or placebo; Treatment Periods will be separated by a washout interval of at least 14 days. Randomization will be stratified by age (<65 years vs. ≥ 65 years). Within each age stratum, subjects will be randomized to 1 of the 3 treatment sequences. Subjects will then enter Treatment Period 1. Procedures and assessments to be conducted during the Randomization Phase are detailed in [Table 5](#).

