3.2 Overall Study Design and Plan

HV Cohort

The HV Cohort comprises a randomized, double-blind, placebo-controlled, 3-period crossover study. Eligible healthy adult and elderly subjects will be randomized to treatment sequence A, B or C, each consisting of 3 Treatment Periods, each of one night's duration, in which subjects will receive a single dose of lemborexant 10 mg, or lemborexant 25 mg, or placebo; Treatment Periods will be separated by a washout interval of at least 14 days. A sufficient number of subjects will be randomized to ensure that 8 evaluable adult subjects (<65 years) and 4 evaluable elderly subjects (≥65 years) complete the study.

Treatment Sequence	Treatment Periods in the HV Cohort		
	1 (one night)	2 (one night)	3 (one night)
A	lemborexant-matched placebo	lemborexant 10 mg	lemborexant 25 mg
B	lemborexant 10 mg	lemborexant 25 mg	lemborexant-matched placebo
C	lemborexant 25 mg	lemborexant-matched placebo	lemborexant 10 mg

OSA Cohort

The OSA Cohort comprises a randomized, double-blind, placebo-controlled, 2-period crossover study.

Adult and elderly subjects with mild OSA will be randomized to treatment sequences D or E, each consisting of 2 Treatment Periods, each of 8 nights' duration, in which subjects will receive lemborexant 10 mg or placebo. The Treatment Periods will be separated by a washout interval of at least 14 days. A sufficient number of subjects will be randomized to ensure that 20 evaluable adult subjects (<65 years) and 10 evaluable elderly subjects (≥ 65 years) complete the study.

Treatment Sequence	Treatment Periods in the OSA Cohort	
	1 (eight nights)	2 (eight nights)
D	lemborexant-matched placebo	lemborexant 10 mg
E	lemborexant 10 mg	lemborexant-matched placebo

Phases of the Study (HV and OSA Cohorts)

For both the HV and OSA cohorts, there will be 2 phases, Prerandomization and Randomization. The Prerandomization Phase for both cohorts will consist of the Screening Period (up to 21 days) and a Baseline Period (≤ 1 day prior to randomization).

For the HV Cohort, the Randomization Phase will comprise 3 Treatment Periods, each of 1-day duration, separated by a washout interval of at least 14 days, followed by a 14-day Follow-Up Period.

For the OSA Cohort, the Randomization Phase will comprise 2 Treatment Periods, each of 8 days duration, separated by a washout interval of at least 14 days, and a Follow-Up Period of 14 days.

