5.3.2 Adjustments for Covariates

Since this is a crossover study, there will be no adjustment for covariates like age, gender, race, ...etc. The model will include fixed effects for sequence, period, and treatment, and a random effect for subject within sequence.

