5.4.1 Primary Pharmacodynamic Analyses

Analysis for the Primary Endpoint

HV Cohort: Mean SpO₂ during TST will be analyzed using a mixed effect model. The model will include fixed effects for sequence, period, and treatment, and a random effect for subject within sequence. The following will be presented: least squares (LS) means, difference in LS mean of lemborexant 10 mg and lemborexant 25 mg compared to placebo, a two-sided 90% CI (equivalent to a one-sided lower 95% CI) for the true mean difference (lemborexant – placebo) in SpO₂ and *p*-value. If the lower bound of the one-sided 95% CI of the treatment difference of SpO₂ is less than -5, this will provide evidence that the given dose of lemborexant does not result in a clinically significant decrease in SpO₂ compared to placebo.

OSA Cohort: AHI will be analyzed using a mixed effect model. The model will include fixed effects for sequence, period, and treatment, and a random effect for subject within sequence. The following will be presented: LS means, difference in LS mean of lemborexant 10 mg compared to placebo, a two-sided 90% CI (equivalent to a one-sided upper 95% CI) for the true mean difference (lemborexant – placebo) in AHI and *p*-value. If the upper bound of the one-sided 95% CI of the treatment difference of AHI is less than 5, this will provide evidence that the given dose of lemborexant does not result in a clinically significant increase in AHI with mild OSA compared with placebo.

A sensitivity analysis may also be performed on the primary endpoint where outliers are excluded. Other sensitivity analyses may be explored.

Plots of AHI and SpO₂ treatment difference data (both individual and LS Mean) will be used to explore the results.

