5.4.2 Secondary Pharmacodynamic Analyses

Analysis for the Secondary Endpoints

The continuous secondary endpoints for both cohorts will be analyzed using the same model as the primary endpoint. Treatment comparison will be performed using contrasts.

The proportion of subjects with SpO₂ <90% will be summarized using descriptive statistics. All analyses will be performed separately for each cohort.

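### The example PROC MIXED code in SAP 13.2 contradicts the primary model and the 90% interval stated in SAP 5.3.2 and 5.4.1: a low-severity mismatch that three edits correct

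*SAP*

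**What the plan says.** SAP 5.3.2 gives the model: "The model will include fixed effects for sequence, period, and treatment, and a random effect for subject within sequence". SAP 5.4.1 and protocol 9.7.1.7.2 repeat it for both cohorts. On output, SAP 5.4.1 says "The following will be presented: least squares (LS) means", then lists differences from placebo and, for the OSA Cohort, "a two-sided 90% CI (equivalent to a one-sided upper 95% CI) for the true mean difference". The HV Cohort has the matching lower-bound interval. Each cohort is judged by comparing the relevant 90% limit with its margin.

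SAP 13.2 then shows how PROC MIXED can be used. CLASS lists sequence, patient, period and treatment. The MODEL statement reads "model Response= sequence patient period treatment /solution" and ends with the Satterthwaite option. RANDOM contains patient within sequence. The last statement is "lsmeans drug / pdiff cl e". Nothing elsewhere in the SAP corrects this code.

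**The concern.** The code and the text describe different analyses.

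- **Effect name.** `drug` is not a variable in the model, so as printed the code should return no treatment LS means, differences or limits.
- **Interval level.** `cl` without an alpha value gives 95% limits by SAS default. The decision rule needs 90% limits. SAP section 5 sets a general two-sided 5% level unless otherwise stated, so 95% limits in the output would not look out of place.
- **Fixed patient effect.** The text allows no fixed effect for patient. Putting it in MODEL leaves sequence with no degrees of freedom of its own and makes the random patient term redundant.

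The first error shows itself when the program is run. The other two need not. SAP 5.4.2 uses the same model for the continuous secondary endpoints, so a template taken from 13.2 would reach beyond the primary analysis. At stake are OSA power, if the wrong level is carried through, and the LS means display.

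**Working it through.** SAS was not run. The 95% default and the rejection of an effect that is not in the model are properties of PROC MIXED, not statements in the documents. The rest is arithmetic and design-matrix algebra.

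**1. Reproducing the stated OSA power.** Inputs from SAP section 4: 30 completers, combined within-subject variance 26.96, true difference 1.5, margin 5.

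- SE of the difference = √(2 × 26.96 / 30) = 1.3406, with 30 − 2 = 28 df.
- Noncentrality = (5 − 1.5) / 1.3406 = 2.61.
- With 90% limits, t = 1.7011 and noncentral-t power is 81.6%. The stated figure is 82%.

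The other four rows of the table give 85.4%, 82.0%, 86.4% and 89.7% against the stated 86, 82, 86 and 90. With 95% limits no row reproduces. The sample size was therefore planned on the 90% interval.

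**2. Effect of repairing only `drug`.**

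| OSA, n = 30 | 90% limits (text) | 95% limits (default) |
|---|---|---|
| t, 28 df | 1.7011 | 2.0484 |
| Half-width, t × 1.3406 | 2.28 | 2.75 |
| Estimate must be below | 5 − 2.28 = 2.72 | 5 − 2.75 = 2.25 |
| Power at true difference 1.5 | 81.6% | 71.2% |
| One-sided error at true difference 5 | 5.0% | 2.5% |

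At the planning SE, an observed difference between 2.25 and 2.72 would pass on the stated interval and fail on the default one.

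HV Cohort (SAP section 4: variance 0.315, n = 12, true difference −1, margin −5): SE = √(2 × 0.315 / 12) = 0.229 with 20 df, and the distance to the margin is 4 / 0.229 ≈ 17.5 SE. Power is above 99% at either level.

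**3. Effect of `patient` in MODEL on LS means.** Each patient belongs to one sequence. In every data row, the sequence indicator therefore equals the sum of the indicators of that sequence's patients, and any estimable combination must keep this equality. An LS mean gives each of S sequences weight 1/S and each of n patients weight 1/n. It can be estimable only if n_s / n = 1/S for every sequence, that is, with equal sizes.

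- OSA 15/15: 15/30 = 1/2, condition met. OSA 16/14: 16/30 = 0.533, not met.
- HV 4/4/4: 4/12 = 1/3, condition met. HV 5/4/3: 5/12 = 0.417, not met.

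Rank checks on the full design matrices agree. With `patient` in MODEL, treatment LS means are estimable at 15/15 and 4/4/4 and not at 16/14, 17/13, 5/4/3 or 6/3/3. The stated model gives them in all six layouts, and the treatment difference is estimable in all six.

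**4. Whether unequal sizes can arise.** Protocol 9.1.1.2 says "Within each age stratum, subjects will be randomized to 1 of the 3 treatment sequences", and the target is "8 evaluable adult subjects (<65 years) and 4 evaluable elderly subjects". Neither 8 nor 4 divides by 3. Block size is not given, so the following is illustrative. It assumes independent permuted blocks by stratum, exactly the planned completers, and no replacements.

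- HV, blocks of 3: adults split 3/3/2 and elderly 2/1/1. Totals are 4/4/4 only when the sequence short in adults is the one doubled in the elderly (1 in 3), and otherwise 5/4/3 (2 in 3, 67%).
- HV, blocks of 6: the chance of 4/4/4 is 17/75 = 0.227, so 77% unequal.
- OSA (20 and 10): unequal in 0%, 33% and 56% of cases with blocks of 2, 4 and 6.

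**5. Effect of `patient` on the decision bound.** With complete data the estimated treatment difference is the same in both models. The SE is also the same (OSA 1.3406 at 15/15; HV 0.2291 at 4/4/4 and 0.2316 at 5/4/3) provided the estimated between-subject variance is positive. If that estimate is zero, the stated model pools the two error strata, and its SE and df differ. Screening AHI is restricted to 5 to <15. For an assumed between-subject variance of 10² / 12 = 8.3 (uniform over that range), within-subject variance 26.96 and n = 30, the estimate is zero in about 10% of simulations.

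**The case against.** The strongest reply is that 13.2 is headed as an example, while the binding model and interval are stated clearly and consistently in the SAP and the protocol. SAP sections 9 and 11 place derivation rules, dataset specifications and table shells in separate documents, so the appendix may never drive production output. As printed, the code gives no interval at all. The 71.2% therefore describes a program in which someone repaired `drug` and overlooked the level in 5.4.1. The chance of unequal HV sizes depends on inputs that the documents do not give. With blocks of 3, for example, 9 adults and 3 elderly would always balance, while 9 and 4 never would. The replacement rule does not say which sequence a replacement receives.

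All of this stands, and it sets the severity. It does not remove the contradiction, because none of the documents provided corrects the code.

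A reader might infer more: that the primary analysis will be run wrongly, that the OSA Cohort is underpowered, or that a false safety claim becomes easier. The documents support none of these. The text governs, and the planned 82% reproduces on the 90% interval. The default 95% interval makes a safety claim harder. With complete data the fixed patient term leaves the estimated difference unchanged, and its SE too, subject to the variance condition above.

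**Conclusion.** The code in SAP 13.2 contradicts the stated primary analysis in three places: the effect named in LSMEANS, the missing interval level, and the fixed patient effect. This is a low-severity code-text mismatch, not evidence of a wrong analysis.

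The power loss, about 10 percentage points in the OSA Cohort and practically none in the HV Cohort, is conditional on a partial repair of the code. It rests on the SAS default and on the SAP's planning variance. The loss of treatment LS means is conditional on `patient` staying in MODEL and on unequal sequence sizes. That can readily happen in the HV Cohort, but how often cannot be determined without the block size and replacement rule.

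**What to change.** Leave the CLASS statement as it is and replace the remaining statements with:

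```
model Response = sequence period treatment / solution ddfm=satterth;
random patient(sequence);
lsmeans treatment / pdiff cl alpha=0.10 e;
```

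Take the reported differences against placebo; `diff=control` with placebo as the reference is one way. The cost is an edit to a SAP appendix before database lock. It needs no new data and does not change the stated analysis.

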13.3 SAS Code Example for Proc Logistic

The following statements use the LOGISTIC procedure to fit a two-way logit with interaction model for the effect of Treatment and AgeGroup, with Age as covariate. The categorical variables Treatment and Sex are declared in the CLASS statement.

```
proc logistic data=XXXX;
class Treatment AgeGroup;
model Binary_Response= Treatment Treatment*AgeGroup AgeGroup / expb;
run;
```

Programming Note: **EXPB option** displays the exponentiated values of the parameter estimates in the “Analysis of Maximum Likelihood Estimates” table for the logit model. These exponentiated values are the estimated odds ratios for the parameters.

SIGNATURE PAGE

Investigational Product Name: E2006/Lemborexant

SIGNATURES	
Authors:	
<hr/> 
PPD [Redacted] PPD [Redacted] [Redacted] Neuroscience Business Group Eisai Inc.
	Date
<hr/> 
PPD [Redacted] PPD [Redacted] [Redacted] Neuroscience Business Group Eisai Inc.
	Date
<hr/> 
PPD [Redacted] PPD [Redacted] [Redacted] Neuroscience Business Group Eisai Inc.
	Date
<hr/> 
PPD [Redacted] PPD [Redacted] [Redacted] Neuroscience Business Group Eisai Inc.
	Date
